#### 7.2.1.2. Subgroup Analysis

The randomization for this study is planned to be stratified by gender; therefore, all descriptive analyses discussed in Section 7.2.1 will additionally be performed stratified by gender.

#### 7.2.1.3. Multicenter Studies

Up to 4 centers are expected for this study and the number of patients at each center by cohort is not expected to be large enough to produce meaningful summaries by center; therefore analyses by center will not be performed.

#### 7.2.1.4. Hypothesis Testing and Significance Level

A two-sided Type I error rate of 0.05 will be used to define statistical significance. The primary endpoint will be met if the null hypothesis is rejected for both comparisons described in Section 7.2.1 at a significance level of 0.05, i.e. both p-values <0.05. For the primary endpoint, a fixed sequence testing procedure will be used to control the Type I error rate. Statistical adjustment of p-values will not be performed.

#### 7.2.1.5. Sensitivity Analyses

The change in PPi from Baseline to pre-3rd dose Week 9 will also be analyzed using analysis of covariance (ANCOVA), with treatment as fixed factor, baseline PPi, gender, baseline weight group ( $\geq$  median versus < median), and study drug lot assignment as covariates, and using both LOCF and OC methods in the FA Set.

The tests will compare 2.0 mg/kg cohort to 0.5 mg/kg cohort, and 3.0 mg/kg cohort to 0.5 mg/kg cohort. Ninety-five percent CIs will be presented together with the estimated p-values.

In addition, sensitivity analyses will be performed if any medications are administered to the patient that might impact the results used in the primary analysis of PPi.

Sensitivity analyses may be employed that include only the patients that receive 100% of the study drug doses through Week 9, as specified in the protocol.

Finally, sensitivity analyses may be employed to exclude biologically implausible outliers in PPi and PLP.

#### 7.2.2. Secondary Endpoint

For the secondary endpoint, PLP change from Baseline to pre-3rd dose Week 9, similar methods as for PPi will be employed in the FA Set and PP Set.

Sensitivity analyses for PLP may be employed for any patients without taking any vitamin B6 or with consistent input of vitamin B6, defined as taking same dose of vitamin B6 during the study. Vitamin B6 usage will be obtained from the concomitant medications.

Additionally for sensitivity, the within-patient mean absolute levels of the pre-treatment "fasting" PLP samples (-168 h, -24 h, pre-dose Day 1) and the "non-fasting" PLP samples (-156 h, -12 h) will be compared using the exact Wilcoxon rank-sum test for all patients in the FA Set. If a statistical difference is detected between the pre-treatment "fasting" and "non-fasting" samples, given samples on treatment are collected under both "fasting" and "non-fasting"

conditions, the change to each post-treatment timepoint will be evaluated descriptively using the matched "fasting" or "non-fasting" average at Baseline; accordingly, "fasting" post-treatment samples will use a "fasting" Baseline and "non-fasting" post-treatment samples will use a "non-fasting" Baseline.

Please refer to Table 4 on how to handle the values fall under the lower limit of quantification (LLOQ).

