#### 7. STUDY POPULATION

#### 7.1. Inclusion Criteria

Patients must meet all of the following inclusion criteria to be eligible for participation in this study:

- 1. Patients or their legal representative(s) must provide written informed consent prior to undergoing any study-related procedures
- 2. Patient has pediatric-onset HPP, defined as onset of first sign(s)/symptom(s) of HPP prior to 18 years of age
- 3. Patients must have a documented diagnosis of HPP as indicated by a documented history of HPP-related skeletal abnormalities and 1 or more of the following:
  - Documented TNSALP gene mutation(s) from a certified laboratory
  - Serum ALP level below the age-adjusted normal range AND plasma PLP above the upper limit of normal at Screening.

NOTE: Historical results from a certified laboratory for PLP may be used to determine patient eligibility. The criterion for plasma PLP is not applicable if the patient is receiving pyridoxine treatment.

- 4. Patients must have a plasma PPi level of ≥3.9 μM at Screening
- 5. Patients must be  $\geq$ 18 years of age at Screening
- 6. Sexually active male and female patients of childbearing potential must agree to use a highly effective method of birth control during the study and for 3 months following the last dose of study drug. Male patients must also not donate sperm during the Screening and treatment periods and for at least 3 months after the last dose of asfotase alfa. Highly effective contraceptive methods are as follows:
  - a. Combined (estrogen and progestogen containing) hormonal contraception associated with inhibition of ovulation:
    - Oral
    - Intravaginal
    - Transdermal
  - b. Progestogen-only hormonal contraception associated with inhibition of ovulation:
    - Oral
    - Injectable
    - Implantable
  - c. Intrauterine device
  - d. Intrauterine hormone-releasing system
  - e. Bilateral tubal occlusion

- f. Vasectomy with documented medical assessment of surgical success
- g. Condom and spermicide
- 7. Female patients of childbearing potential must have a negative pregnancy test at the time of enrollment
- 8. Female patients not of child-bearing potential due to surgical sterilization (at least 6 weeks after surgical bilateral oophorectomy with or without hysterectomy or at least 6 weeks after tubal ligation) confirmed by medical history, or menopause
  - a. Menopausal women include women with either

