#### 5.1.2. Secondary Endpoint

The change in pyridoxal 5'-phosphate (PLP) from Baseline to pre-3rd dose Week 9. Baseline is defined as the average of all available pre-dose assessments prior to first SC injection with asfotase alfa (-168, -156, -24, -12h, and pre-dose Day 1). Pre-3rd dose Week 9 is defined as the value obtained prior to the 3rd dose during Week 9.

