Abbreviations: EOS = end-of-study; F/U = follow-up; AE = adverse event; HR = heart rate; IAR = injection-associated reaction; PK = pharmacokinetics; PLP = pyridoxal 5'-phosphate; PPi = inorganic pyrophosphate; PTH = parathyroid hormone; m = month; W = Week; d = day.

**NOTE:** Patients may be asked to provide additional blood samples at an unscheduled visit at the request of the Sponsor or Investigator as part of a safety evaluation or for adjustment of the drug dose.

 The Safety Follow-Up Call will occur 3 months after the last dose of study drug. Males and Females of child-bearing potential will be followed up for birth control and pregnancy information. Any reported pregnancies in female patients or female partners of male patients will be followed until the outcome of the pregnancy is known. Refer to Section 9.4.1.10 for further details.

 The Week 1, Day 1 single dose must be administered on a Monday, and the multiple dosing must be administered on Mondays, Wednesdays, and Fridays during the weeks indicated.

 To facilitate scheduling of required study assessments at each visit, the study visit may be shortened or prolonged, as necessary, as long as the specified order of assessments and/or availability of results pertaining to laboratory work (including PK and pregnancy and asfotase alfa anti-drug antibody testing) and vital signs are adhered to.

 If the time period between the initial Screening and the re-Screening is >12 weeks, all Screening procedures must be repeated.

 Demographics will be collected as permitted by region and may include Date and region of birth, age, sex, ethnicity, race, and whether the patient is of Japanese descent.

 Medical history includes general medical history and HPP-specific medical history from historical medical records (eg, X-rays, videos, hospitalization records). Details of loss of adult teeth will be included as part of medical history.

 HPP gene mutation analysis will be performed at Baseline if results (from within 49 days of Baseline) are not available in the medical records.

 Concomitant medications and therapies must be collected from 30 days prior to study entry up until the final study visit. All available historical use of certain medications (ie, related to HPP, growth, etc.) will be captured.

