#### Medications and Therapies:

Concomitant medications/therapies are any events with administration dates and times on or after the date and time of the first study drug dose. If the start date of a medication or therapy is partially or completely missing and the end (stop) date and time of the medication/therapy does not indicate that it occurred prior to first dose, then the determination of concomitant status will be based on the following:

If the start year is after the year of the first study drug dose, then the medication/therapy is concomitant; else,

If the start year is the same as the year of the first study drug dose and the start month is missing, then the medication/therapy is concomitant; else if the start month is present and is the same or after the month of the first study drug dose, then the medication/therapy is concomitant; else, if the start date is completely missing, then the medication/therapy is concomitant.

All other medications/therapies are considered prior medications/therapies and could occur from the 30 days prior to informed consent up through the Run-In Period and prior to the 1st dose.

Normal Reference ranges for PPi and PLP:

PPi (μM):	
Male/Female	
13-18 years 0.75-4.78	
>18 years 1-5.82	

PLP (ng/mL):
Male/Female
6-18 years 5.74-61.15
>18 years 2.81-26.70

For observations that fall under the lower limit of quantification (LLOQ), the following values will be used:

Table 4:	Values	Used for	Observat	tions under	the Lower	Limit o	of Q	uantification	(LLOC	))
----------	--------	----------	----------	-------------	-----------	---------	------	---------------	-------	----

Parameter	Value Used
Plasma PPi	0.75µM
Plasma PLP	2.5ng/mL
Serum PTH	.5 x LLOQ

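### The vitamin B6 sensitivity set for PLP is read from concomitant medications only, so B6 taken during the baseline samples and stopped before first dose is not seen

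*SAP*

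**What the plan says.** The secondary endpoint is the change in PLP from Baseline to the sample before the third dose of Week 9 (Day 61). On Baseline, SAP 5.1.2 states: "Baseline is defined as the average of all available pre-dose assessments prior to first SC injection with asfotase alfa". It lists five samples: -168, -156, -24 and -12 h, and pre-dose Day 1.

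SAP 7.2.2 provides an optional check on B6: "Sensitivity analyses for PLP may be employed for any patients without taking any vitamin B6 or with consistent input of vitamin B6". Consistent input is "defined as taking same dose of vitamin B6 during the study". The data source is given in one sentence: "Vitamin B6 usage will be obtained from the concomitant medications".

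SAP 9.3, under Medications and Therapies, gives the analysis definition: "Concomitant medications/therapies are any events with administration dates and times on or after the date and time of the first study drug dose". The remainder is covered by the next rule: "All other medications/therapies are considered prior medications/therapies and could occur from the 30 days prior to informed consent up through the Run-In Period".

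The protocol allows for patients on pyridoxine. The note to inclusion criterion 3 in Protocol 7.1 reads: "The criterion for plasma PLP is not applicable if the patient is receiving pyridoxine treatment". The exclusion criteria in Protocol 7.2 neither bar B6 nor require a stable dose.

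**The concern.** The endpoint is a difference between two measurements. A check for B6 confounding has to know B6 use at both ends: while the baseline samples are drawn and up to the Day 61 sample. The SAP takes B6 use from a category that begins at first dose, when the whole baseline has already been collected.

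This opens two routes for misclassification, even when every date is known:

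- A patient takes B6 during some of the baseline samples and stops before first dose. The record is prior, so the patient enters the set as someone who took no B6.
- A patient changes B6 dose during run-in and holds the new dose from Day 1. Only the new dose is concomitant, so the patient can enter the set as a consistent user.

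In both cases B6 exposure differs between Baseline and Day 61, which is the situation the set is meant to exclude. With 6 to 9 patients per cohort, one such patient carries visible weight, and the check could reassure when it should not.

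**Working it through.** The documents give no figure for PLP or B6 to reproduce. The check applies the SAP's definitions to a timeline and then expresses the effect in terms of an unknown.

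**Inputs**
- Baseline sample times: -168, -156, -24, -12 h and pre-dose Day 1, taken as 0 h (SAP 5.1.2).
- Cut-off for concomitant: first dose, 0 h (SAP 9.3).
- Cohort size n: 9 planned (SAP 9.2), 6 as the minimum completing (Protocol 6.1).
- D: rise in one PLP sample while on B6. This is an assumption without a value, because the documents give none.

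**Step 1: classification.** Let k be the number of baseline samples drawn on B6.

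| B6 stopped at | Class under SAP 9.3 | Status in the set | k of 5 |
|---|---|---|---|
| -170 h | prior | non-user | 0 |
| -160 h | prior | non-user | 1 |
| -100 h | prior | non-user | 2 |
| -20 h | prior | non-user | 3 |
| -6 h | prior | non-user | 4 |
| +10 h | concomitant | user | 5 |

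**Step 2: shift in the patient's Baseline.** Shift = kD/5. For k = 1 to 4 this is 0.2D to 0.8D. Change is Day 61 minus Baseline, so the patient's apparent fall in PLP is larger by the same amount.

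**Step 3: shift in the cohort mean change from one such patient.** Shift = kD/(5n).
- n = 9: 1/45 = 0.022D up to 4/45 = 0.089D.
- n = 6: 1/30 = 0.033D up to 4/30 = 0.133D.

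These are shifts in the unadjusted mean change, with all n patients in the set. If other B6 users have been removed, n is smaller and the shift larger. Carry-over of B6 after stopping would also enlarge it. A model adjusted for baseline PLP would give a different figure, which cannot be computed from the documents.

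**Step 4: with the window corrected.** If B6 use is read from prior and concomitant records from -168 h through Day 61 pre-dose, the patients in the four rows from -160 h to -6 h are neither non-users nor on a constant dose, and they leave the set. No sample size or power figure changes.

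**The case against.** The best counter-argument is that the SAP uses the term concomitant medications in two ways. In the schedule of events (SAP Appendix 9.1, Table 2) the row is ticked at Screening and Run-in, and footnote 8 says: "Concomitant medications and therapies must be collected from 30 days prior to study entry up until the final study visit". If SAP 7.2.2 simply names that record as its data source, run-in B6 is visible. The phrase about the same dose during the study could also cover run-in, since the protocol synopsis counts the run-in week in its 13.5 weeks. SAP 7.3.1 starts study duration at first dose, but only for the exposure summary.

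This shows that the data exist; it does not remove the problem. Footnote 8 is a collection rule, whereas SAP 9.3 is the analysis definition. SAP 7.1.4 treats prior and concomitant as separate terms, and SAP 7.2.2 names only one of them. A programmer following SAP 9.3 would omit run-in use.

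Other limits stand. Nothing in the protocol prompts a patient to stop B6 in the run-in week, and the documents give no frequency for it. Both prior and concomitant medications are listed by patient, so a reader of the listings could spot such a case.

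Some stronger readings are tempting but not supported:

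- *The protocol regards PLP as uninterpretable under B6.* Protocol 7.1 waives one eligibility criterion and gives no reason, direction or size. With the existence of the sensitivity analysis, this is only indirect evidence that B6 matters.
- *This is the only protection for PLP.* SAP 7.2.1.5 requires sensitivity analyses for PPi if medications might affect the result, and SAP 7.2.2 applies similar methods to PLP, so that provision may carry over. It sets no B6 window, however.
- *The set wrongly drops patients whose B6 changes after Day 61.* Methods carried over from SAP 7.2.1 summarize change at all timepoints from Week 1 to Week 13. For those summaries, later B6 use is relevant.

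**Conclusion.** The concern holds as a defect in a stated rule. On the SAP's own definitions, B6 use confined to the baseline period is classed as prior, and the patient counts as a non-user in the set intended to be free of B6 effects. A dose changed in run-in can likewise pass as consistent.

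The classification result does not depend on D. The size does, together with the assumptions of no carry-over and one affected patient per cohort. A reader might infer a shift in ng/mL that is large against the adult normal range in SAP 9.3. The documents supply no B6 effect from which to calculate one, and a shift of D/n would be an upper case in which all five baseline samples carry the full effect.

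The consequence is modest. It is limited to an optional sensitivity analysis of the secondary endpoint. The primary PPi analysis and its fixed-sequence testing are untouched. The main PLP analysis does not select patients by B6 use, so this rule does not alter it.

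**What to change.** Amend SAP 7.2.2 before the analysis:

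1. Take B6 use from both prior and concomitant medication records.
2. For the Week 9 PLP endpoint, define no B6 and same dose over the window from the first baseline sample (-168 h) through the Day 61 pre-dose sample. If the sponsor wants to allow for carry-over, add a short lead-in of pre-specified length.
3. For descriptive summaries at later timepoints, extend the window to the timepoint concerned.

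The window should not start 30 days before study entry merely because collection does. Screening can begin at Week -12, and 30 days is about 4 weeks, so the window could reach back about 16 weeks before Day 1. It would then remove patients whose B6 use had been stable since well before -168 h. Whether the analysis stays optional is the sponsor's choice; the correction does not depend on it.

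The cost is a few sentences in the SAP. Medications are already collected from 30 days before study entry, so no new data are needed. The downside is that a patient who changed B6 during run-in leaves this optional set, which makes small cohorts slightly smaller in that analysis only.

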#### **Number of Patients Planned:**

Screened: 36 Randomized: 27

Completed: 18 (minimum)

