- Screening serum creatinine or parathyroid hormone (PTH) levels ≥1.5 times the upper limit of normal is an exclusion criterion.
- All prior and concomitant medications and therapies must be collected from 30 days prior to study entry up until the final study visit. The protocol has inconsistent description of the process for the collection of Concomitant medications and therapies in Table 2, footnote 9 and Section 8.7.
- All pre-dose PK/PD/ADA samples during the Run-in Period and Main Study Period (Treatment Period) must be collected under fasting conditions, except for Day -7, -156 hour and Day -1, -12 hour samples. The post-dose PK/PD/ADA samples will not be collected under fasting conditions.
- Effective March 3rd, 2016, the Drug Safety Physician of this protocol is

Title: PPD Email: PPD

Phone number: PPD

If there are any questions concerning this change, please contact PPD by phone at PPD or by email at PPD This change will be captured in the next protocol amendment.

Sincerely.	PPD	
PPD		

Alexion Pharmaceuticals, Inc. [name]

Cc: eTMF, ISF
PPD Project Manager

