As supportive analysis, the non-parametric exact Wilcoxon rank-sum test will be used to assess differences between treatment cohorts, using both last observation carried forward (LOCF) and observed case (OC) methods. The location shift in the change from Baseline distributions and 95% CI for the above comparisons will be reported using the Hodges-Lehmann-Sen estimate and the exact confidence limits reported.

To examine the change from Baseline in PPi, descriptive statistics for the absolute PPi level and the change from Baseline will be summarized at all study timepoints by treatment cohort, spanning from Week 1 to Week 13; Baseline will be calculated in the same way as for the primary analysis. Within cohort, the change from Baseline to all study timepoints will be analyzed using the non-parametric Wilcoxon signed-rank test.

Individual and mean PPi levels for each cohort versus time curves will be presented with normal references ranges indicated (see Appendix 9.3). Please refer to Table 4 on how to handle the values fall under the lower limit of quantification (LLOQ). Additional analysis of PPi data may be performed if considered useful.

The above analyses for PPi will additionally be performed using the PP Set.

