#### **Definition of Treatment Baseline:**

• For PPi and PLP assessments, there are 5 pre-treatment baseline samples (-168, -156, -24, -12h, and pre-dose Day 1) to be collected. The average value will be used for Baseline.

• For antibody, and laboratory assessments, Treatment Baseline is the Day 1 pre-dose sample.

• For Safety assessments (including weight), the last assessment prior to first dose will be used for Treatment Baseline.

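### The fasting versus non-fasting PLP check in SAP 7.2.2 uses a test for independent groups on paired patient means

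*SAP*

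**What the plan says.** Each patient is scheduled to give five PLP samples before the first dose. SAP Appendix 9.3 states that "there are 5 pre-treatment baseline samples (-168, -156, -24, -12h, and pre-dose Day 1) to be collected". Administrative Change Letter #2 requires pre-dose samples to be taken fasting, "except for Day -7, -156 hour and Day -1, -12 hour samples". So every patient is planned to have three fasting samples (-168 h, -24 h, pre-dose Day 1) and two non-fasting samples (-156 h, -12 h).

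SAP 7.2.2 averages each type within the patient and says the resulting levels "will be compared using the exact Wilcoxon rank-sum test for all patients in the FA Set". If a difference is found, "the change to each post-treatment timepoint will be evaluated descriptively using the matched" fasting or non-fasting Baseline. The summary is conditional on the test result.

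Elsewhere the SAP separates the two Wilcoxon tests. In 7.2.1 the rank-sum test compares treatment cohorts, which are independent groups. For change within a cohort, "the change from Baseline to all study timepoints will be analyzed using the non-parametric Wilcoxon signed-rank test".

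**The concern.** The rank-sum test takes its reference distribution from two unrelated samples. Here a patient with a high PLP level will tend to be high under both conditions. The test counts that between-patient spread as noise, although it cancels when each patient is compared with himself or herself. The SAP gives no paired version of this check and no reason for an unpaired one.

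The check asks whether fasting status disturbs PLP, so the harmful error is to miss an effect. With all five samples present, Baseline is (3F + 2N)/5 = F + 0.4(N - F), where F and N are the fasting and non-fasting levels. A real difference therefore enters Baseline at two fifths of its size. The matched-baseline summary is the SAP's means of showing this, and it appears only if the test is significant.

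**Working it through.** **Plan's own figure.** None: the documents give no power or sample size for this check.

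**Inputs from the documents.** Two-sided 0.05 level (SAP 7); 27 patients planned, and 18 as the planned minimum of completers (Protocol synopsis). The 18 is used as a low case, since the FA Set may be larger.

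**Assumptions.** Correlation ρ between a patient's two means of 0.3, 0.5, 0.7 or 0.9; shift of 0, 0.3, 0.5 or 0.8, in SD units of the patient means; bivariate normal means with a common SD.

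**Why the direction is fixed.** For a difference of two means over n patients, the variance is 2σ²(1 - ρ)/n. An unpaired method works as if it were 2σ²/n, so its standard error is too large by 1/√(1 - ρ): 1.20, 1.41, 1.83 and 3.16 for the four correlations. The same mechanism acts on ranks.

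**Exact critical values (two-sided).**
- n = 27: rank-sum U ≤ 250 (4.80%); signed-rank W ≤ 107 (4.91%).
- n = 18: rank-sum U ≤ 99 (4.71%); signed-rank W ≤ 40 (4.83%).

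**Rejection rates, rank-sum / signed-rank, in %** (100,000 simulated trials per cell).

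n = 27:

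| Shift (SD) | ρ = 0.3 | ρ = 0.5 | ρ = 0.7 | ρ = 0.9 |
|---|---|---|---|---|
| 0 | 2.1 / 5.0 | 0.7 / 5.0 | 0.1 / 5.0 | <0.1 / 5.0 |
| 0.3 | 14.1 / 23.5 | 10.9 / 31.0 | 6.7 / 47.3 | 2.0 / 90.6 |
| 0.5 | 39.9 / 54.0 | 38.5 / 68.4 | 37.0 / 88.4 | 36.4 / >99.9 |
| 0.8 | 83.9 / 91.1 | 87.3 / 97.5 | 92.1 / 99.9 | 98.3 / >99.9 |

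n = 18:

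| Shift (SD) | ρ = 0.3 | ρ = 0.5 | ρ = 0.7 | ρ = 0.9 |
|---|---|---|---|---|
| 0 | 2.0 / 4.8 | 0.8 / 4.8 | 0.1 / 4.9 | <0.1 / 4.8 |
| 0.3 | 9.2 / 16.5 | 6.8 / 21.3 | 3.8 / 32.7 | 1.0 / 74.2 |
| 0.5 | 25.8 / 37.6 | 22.6 / 49.3 | 19.3 / 71.1 | 14.9 / 99.2 |
| 0.8 | 63.4 / 75.0 | 65.3 / 87.5 | 69.7 / 98.0 | 78.5 / >99.9 |

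**Second model.** Three fasting and two non-fasting samples were simulated per patient with a shared patient effect (40,000 trials per cell). For single-sample intraclass correlation c, the correlation between the two means is c / √[(c + (1 - c)/3)(c + (1 - c)/2)]. At c = 0.5 this is 0.5/√(0.667 × 0.75) = 0.71. Shifts here are in single-sample SDs, so the percentages cannot be compared directly with those above. For n = 27 and a shift of 0.5:
- c = 0: 77.0% rank-sum, 76.0% signed-rank.
- c = 0.5: 58.9% and 96.7%.
- c = 0.8: 46.8% and >99.9%.

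The tests perform alike only when a patient's samples are uncorrelated.

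**Does the replacement hold its level on skewed data?** Lognormal samples were simulated with no true difference, mean of three against mean of two, log SD 0.3 to 1.0, intraclass correlation 0.5 to 0.9, and n = 18 and 27 (20,000 trials per cell). The signed-rank error was 4.6% to 5.4%.

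**The case against.** The strongest reply is that very little depends on this p-value. SAP 7.2.2 presents the check as a sensitivity step below a secondary endpoint, and its only consequence is descriptive. The endpoint keeps its definition under either test: in SAP 5.1.2, "Baseline is defined as the average of all available pre-dose assessments prior to first SC injection with asfotase alfa". The primary PPi analysis is not involved, and all cohorts share the same planned 3:2 mix of samples. The error also runs one way: with positive correlation the test misses differences rather than inventing them. All of this stands, and it limits the point to a minor one. It does not make the test right, because missing a difference is the error this check should avoid.

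A second reply is that the size of the loss is assumed. This also stands. At a correlation of 0.1 with 27 patients, the rank-sum error is 3.8% and power at 0.5 SD is 41% against 45%, so the loss is slight. It becomes marked from about 0.5 upward. Large shifts are usually found anyway: at 0.8 SD with 27 patients the rank-sum test detects 84% to 98%. The skewed-data check covers error rate only, not power.

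A third reply is that a paired test drops any patient lacking one type of sample, whereas the SAP names the whole FA Set, and entry to that set requires only one pre-treatment PPi result. That is a real change of analysis set, but with five scheduled samples it should rarely matter.

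**Conclusion.** The concern holds, as a minor one. The mismatch between paired data and an independent-groups test follows from the documents and needs no assumption. The direction of the error requires only positive correlation between a patient's two means, which is what one would expect from repeated samples taken within a week.

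The percentages are illustrative. They depend on the assumed correlation, shift and normal model, and they cannot be put on the PLP scale because the documents give no PLP SD for these patients. Within the assumed range, the loss is substantial for small to moderate differences and mostly small for large ones with 27 patients. The practical result is that a real fasting difference may be reported as not detected and one planned descriptive summary omitted.

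**What to change.** In SAP 7.2.2, replace the exact Wilcoxon rank-sum test with the exact Wilcoxon signed-rank test on each patient's fasting mean minus non-fasting mean. State that the test uses FA Set patients who have both means. This matches how SAP 7.2.1 handles other within-patient comparisons.

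Two additions are worth considering but are not needed to correct the error:
- Report the Hodges-Lehmann estimate of the difference with its 95% CI, so the reader sees its size as well as a p-value.
- Present the matched-baseline PLP summary whatever the p-value, so that the test only describes the difference.

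The correction is a one-line SAP edit before database lock. It needs no new samples, visits or tables. The estimate and CI would add one line to the existing output; the second option would make a summary that is now conditional a routine one.
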